8.1 Efficacy Assessments

The Study Reference Manual provides detailed information for the various scales discussed in Section 8.1.1 through Section 8.1.6.

8.1.1 Efficacy Endpoint Scales

- The ESS is a self-administered questionnaire with 8 questions. Respondents are asked to rate, on a 4-point scale (0-3), their usual chances of dozing off or falling asleep while engaged in 8 different activities in recent times. The ESS score (the sum of 8 item scores, 0-3) can range from 0 to 24. The higher the ESS score, the higher that person's average sleep propensity in daily life, or their 'daytime sleepiness'. The questionnaire takes approximately 2 or 3 minutes to answer. The ESS is asked during screening as an enrollment criterion. The ESS is also used as a study efficacy outcome. The ESS is administered the day of the non-PSG screening and approximately the same time of day prior to PSG recordings.

- The Participant Global Impression of Severity (PGI-S) is a global index that may be used to rate the severity of a specific condition, (i.e., it is a single-state scale). The scale consists of a 1-item questionnaire designed to assess the participant's impression of disease severity. The scale is considered to have clinical relevance for the participant because it allows participants to respond based on factors that they judge to be the most important in their health status. The PGI-S is administered at the baseline/screening PSG Visit 2 and at PSG Visit 4. The PGI-S is administered at approximately the same time prior to each PSG recording.
- The Participant Global Satisfaction with Treatment scale consists of a 1-item questionnaire designed to assess the participant's satisfaction with the experimental treatment, considering both safety and efficacy. The scale is administered at the end of the study, at the EOS Visit.

8.1.2 Safety and Abuse Liability Scale

- The Cocaine Selective Severity Assessment (CSSA) was designed to measure cocaine withdrawal signs and symptoms during detoxification, and includes psychiatric symptoms of general safety interest such as changes in sleep, anxiety, energy level, activity level, tension, attention, paranoid ideation, anhedonia, depression, suicidality, and irritability. The CSSA will be used in this study to identify psychiatric issues and to characterize the potential of the atomoxetine/oxybutynin combination to elicit withdrawal symptoms similar to those elicited by cocaine withdrawal. A modified version of the assessment will be used in this study to measure potential withdrawal signs and symptoms from the study treatment; “cocaine” will be replaced with “study drug”. The scale is administered by clinical staff. A score of ≥ 3 on Item 17, or Investigator judgment that the patient is suicidal, will initiate further clinical evaluation and appropriate measures to protect participant safety. (Note: Questions 4 and 5 of the CSSA will not be asked at baseline).

8.1.3 Functional Endpoints

- The Digit Symbol Substitution Test (DSST) is a paper-and-pencil cognitive and psychomotor test that requires patients to identify and copy symbols that are matched to numbers according to an instruction key located at the top of the page. The DSST is commonly used to screen for impairment related to pharmaceuticals and is also sensitive to sleep restriction. The DSST is administered the morning after the inpatient PSG nights, at approximately the same time after awaking from each PSG.

- The Delayed Word Recall Test (DWRT) is a brief and efficient test of verbal learning and recent memory. The DWRT is administered the morning after the screening/baseline PSG (Visit 2) and in the morning after PSG Visit 4. The DWRT is administered at approximately the same time after awaking from each PSG.

8.1.4 Screening/Eligibility Scales

- The IPSS is typically used to diagnose benign prostatic hyperplasia and to monitor disease progression and response to therapy. The participant is asked to choose the rating that best represents their condition. The scale ranges from 1 to 5, with 5 representing the most symptomatic disease and giving an overall maximum possible score of 35. The IPSS is administered to males as an enrollment criterion.
- The STOP-Bang questionnaire has been developed and validated as a screening tool for OSA. The STOP-Bang questionnaire is used in the study only for participants who do not have a previous diagnosis of OSA or use of CPAP, to determine whether there is a high enough pre-test probability of moderate to severe OSA to conduct enrollment screening. The standard STOP-Bang scoring used in the sleep clinic has only moderate specificity. For the purposes of this study, scoring with higher specificity is used (STOP-Bang score ≥ 5 , or $\text{STOP} \geq 2 + \text{BMI} > 35 \text{ kg/m}^2$) to decrease screening participants who are unlikely to meet enrollment criteria.

8.1.5 Polysomnography

- Methods: Standard overnight PSG recording and data interpretation will be performed in accordance with the American Academy of Sleep Medicine (AASM) scoring manual. Participants will be instrumented with standard PSG electrodes. Time of lights out will be established according to the participants' habitual schedule and kept constant across the PSG study nights. The participants will be given 8 hours of time-in bed.
- Technically Adequate Test: The screening/baseline PSG study must meet the following criteria for participants to enroll:
 - At least 4 hours of sleep.
 - At least 2 electroencephalograms (EEGs) and 2 electrooculography traces for the full night.
 - P nasal for at least 60% of the night and thermistor or both respiratory belts signals for the full night for scoring respiratory events.

- At least 30% of sleep in supine position.

Participants who do not have a technically adequate test at baseline can be retested at the discretion of the investigator.

- Scoring: For uses other than study enrollment, all studies will be scored by centralized PSG technologists, blinded to treatment assignment. Baseline and on-treatment PSGs for each individual participant will be scored by the same technologist. Scoring will be conducted according to the American Academy of Sleep Medicine manual scoring criteria.

8.1.6 Home Oximetry

- Participants will be instructed on the at-home use of oximetry at Visit 2 and will be provided with an oximeter that is capable of nightly recording and storage of data for the entire at-home period (study Days 1-11). Participant use of oximeter will be reinforced during the study visit on Day 6 (Visit 3), and through a reminder telephone contact on Day 10. The study personnel will replace the batteries in the oximeter during the Day 6 study visit. The number per hour of oxygen desaturations $\geq 4\%$ will be compared between the average of the baseline nights and the average of the randomized study treatment nights.

8.2 Safety Assessments

- Planned time points for all safety assessments are provided in the SoA.
- Safety monitoring will be guided by the established safety profiles of atomoxetine and oxybutynin, and by Phase 1 safety data for the combination. Safety assessments will include physical examinations, measurement of vital signs, monitoring and recording of AEs, SAEs, and pregnancies, suicidality assessment, recording of study or treatment discontinuations, measurement of ECGs, clinical laboratory evaluations, and memory testing. Effects on OSA and sleep parameters (e.g., sleep time and sleep stages) will also be monitored by PSG.
- Adverse events of special interest include effects on urine outflow, as both atomoxetine and oxybutynin are associated with urinary retention. Effects of atomoxetine on heart rate and blood pressure are expected to be modest, as indicated by the initial data described above, and will also be monitored. Participants with serious cardiac abnormalities will be excluded from the study. Suicidal ideation in children and adolescents is a boxed warning for atomoxetine; however, analysis in adult patients, the target population for the proposed OSA study, did not reveal an increased risk of suicidal ideation or behavior in association with atomoxetine. Safety monitoring in the dose-finding study will use an appropriate questionnaire to monitor for the potential emergence of suicidal ideation or behavior.

- Daytime sleepiness is both a potential safety outcome and efficacy outcome in OSA. Both atomoxetine and oxybutynin are associated with somnolence, and oxybutynin is additionally associated with anticholinergic CNS effects such as memory difficulty. Safety monitoring will therefore include psychomotor vigilance testing and memory testing.

8.2.1 Physical Examinations

- Physical examinations at screening/baseline include anthropomorphic data relevant to OSA: neck circumference at superior border of cricothyroid cartilage; waist circumference at highest point of iliac crest; evaluation of the oropharynx, hypopharynx, and facial skeletal structure; Mallampati score; tonsils evaluation (0-3+); presence of micrognathia; nasal patency.
- The general physical examination at screening/baseline includes an assessment of general appearance and a review of physical systems (dermatologic, head, eyes, ears, nose, mouth/throat/neck, thyroid, lymph nodes, respiratory, cardiovascular, gastrointestinal, extremities, musculoskeletal, neurologic, and psychiatric systems). Height and weight will also be measured and recorded (with shoes removed and wearing light indoor clothing).
- Investigators should pay special attention to clinical signs related to previous serious illnesses.

8.2.2 Vital Signs

- Assessment of vital signs (seated blood pressure, pulse rate, body temperature, respiratory rate) will be performed at the time points indicated in the SoA ([Section 1.3](#)).
- Vital signs will be measured at all visits in a seated position after 5 minutes rest and will include temperature, respiratory rate, systolic and diastolic blood pressure, and pulse. Measurements should be made in the same arm of the participant at each visit.
- Systolic and diastolic blood pressure will be repeated for a total of 3 measurements, each at least 2 minutes apart.
- The method used to measure body temperature at screening should be maintained throughout the study for each participant, and should be indicated (e.g., ear, mouth, armpit).

8.2.3 Electrocardiograms

- A 12-lead ECG will be obtained using an ECG machine that automatically calculates the heart rate and measures the PR, QRS, and QT intervals, and the corrected QT-interval (QTc). The ECG will be recorded in the semi-supine position after the participant has rested in this position for at least 10 minutes.

8.2.4 Clinical Safety Laboratory Assessments

- Refer to [Appendix 10.2 \(Section 10.2\)](#) for the list of clinical laboratory tests to be performed and to the SoA for the timing and frequency.
- The Investigator must review the laboratory report, document this review, and record any clinically relevant changes occurring during the study in the AE section of the eCRF. The laboratory reports must be filed with the source documents. Clinically relevant abnormal laboratory findings are those which are not associated with the underlying disease, unless judged by the Investigator to be more severe than expected for the participant's condition.
- All laboratory tests with values considered clinically significant during participation in the study should be repeated until the values return to normal or baseline. If such values do not return to normal/baseline within a period of time judged reasonable by the Investigator, the etiology should be identified, where possible, and the Sponsor notified.
- All protocol-required laboratory assessments, as defined in [Appendix 2 \(Section 10.2\)](#), must be conducted in accordance with the laboratory manual and the SoA.
- If laboratory values from laboratory assessments not specified in the protocol and performed at the institution's local laboratory result in the need for a change in participant management or are considered clinically relevant by the Investigator (e.g., are considered to be an SAE or an AE or require dose modification), then the results must be recorded in the eCRF.

8.2.5 Suicide Risk Monitoring

Atomoxetine and oxybutynin are CNS-active drugs. There has been concern that some CNS-active drugs may be associated with an increased risk of suicidal ideation or behavior when given to participants with certain conditions or baseline characteristics. Although this study treatment or other similar drugs in this class have not been shown to be associated with an increased risk of suicidal thinking or behavior when given to adults, it is important to monitor for such events during this clinical study.

Suicidal ideation in children and adolescents is a boxed warning for atomoxetine; however, analysis in adult participants, the target population for the proposed OSA study, did not reveal an increased risk of suicidal ideation or behavior in association with atomoxetine.

The CSSA item 17, “suicidality”, will be used to monitor participants for suicidality during the study (whether or not abuse-related). A score of ≥ 3 will be considered an AE and will initiate further clinical evaluation and appropriate measures to protect participant safety. Participants should be monitored appropriately and observed closely for suicidal ideation and behavior or any other unusual changes in behavior. Consideration should be given to discontinuing participants who experience signs of suicidal ideation or behavior. Families and caregivers of participants should be instructed to monitor participants for the emergence of unusual changes in behavior, as well as the emergence of suicidal ideation and behavior, and to report such symptoms immediately to the study Investigator.

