|--|---|---|---|---|---|---|-----------------|--|
| Vital signs ¹² | X | | | | X | X | X | Visit 4 measure both pre-dose and post-awakening from PSG |
| AE/SAE monitoring | X | X | X | X | X | X | X | |
| Study Instruction Reminder | | | | | X | | | |
| Oximeter Battery Change | | | | | X | | | |
| Prior/concomitant medication monitoring | | | | | X | X | X | |
| Inpatient Polysomnography | | X | | | | X | | |
| ESS | X | X | | | | X | | Measured at Visit 1 to determine eligibility and as efficacy outcome on PSG nights; measured evening of baseline PSG and Visit 4 PSG |
| CSSA | X | | | | | X | X ¹³ | Item 17 of the CSSA is used to assess suicidality |
| Patient Global Impression-Severity | | X | | | | X | | Measured evening of baseline PSG and Visit 4 PSG |
| Patient Global Satisfaction with Treatment | | | | | | | X | |
| Home Oximetry | | | X | X | | | | Oximeter used all at-home dosing nights |
| Delayed Word Recall Test | | X | | | | X | | Administer at similar time after awakening after each PSG |
| DSST | | X | | | | X | | Administer at similar time after awakening after each PSG |

Abbreviations: AE = adverse event; CPAP = continuous positive airway pressure; CSSA = Cocaine Selective Severity Assessment; CYP2D6 = cytochrome P450 2D6; DSST = Digit Symbol Substitution Test; ECG = electrocardiogram; EOS = end of study; ESS = Epworth Sleepiness Scale; HIV = human immunodeficiency virus; ICF = informed consent form; IRB = Institutional Review Board; IRT = Interactive Response Technology; OSA = obstructive sleep apnea; PSG = polysomnography; QHS = 1 dose taken at bedtime; SAE = serious adverse event; STOP-Bang = Snoring, Tiredness, Observed apnea, Blood Pressure-Body mass index, Age, Neck circumference and Gender criteria; WOCBP = women of childbearing potential.

- 1 Following pre-screening, participants who meet basic eligibility requirements will be screened during a visit that includes non- PSG evaluations. Participants who otherwise are eligible will be scheduled for an overnight PSG study.
- 2 If a participant discontinues from the study, all EOS procedures should be performed at the discontinuation visit, within 48 hours of the last study dose.

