- 3 Final study eligibility is determined the morning after the PSG exam, based on PSG and non-PSG findings, and enrolled participants are randomized and dispensed the study drug. The first dose of study drug should generally be taken that night; however, at the discretion of the investigator, the first night of study treatment dosing can occur up to 1 week later to accommodate scheduling of the on-drug PSG exam.
- 4 Trial day includes overnight through morning completion of endpoints.
- 5 Daily bedtime dosing (qhs in the protocol synopsis) continues through Visit 4 PSG night, i.e., through PSG visit window; final night of study treatment dosing is PSG night.
- 6 Can occur as late as day as Day 7, if necessary for scheduling.
- 7 Preference is for PSG Visit 4 to be on Day 12, but, if necessary to fit individual participant scheduling, may be \pm 2 days..
- 8 Conducted prior to screening/PSG admission; per IRB-approved pre-screening procedures.
- 9 No trial-related assessment is to be carried out before the participant has signed the ICF. Any participant who provides informed consent will have a screening number assigned by the IRT system.
- 10 Includes amphetamine; barbiturates; benzodiazepines; buprenorphine/metabolite; cannabinoids, cocaine/metabolites; Methylenedioxymethamphetamine; methadone/metabolite; opiates;; phencyclidine; by enzyme-linked immunosorbent assay method; test sample is urine.
- 11 Participants must return to PSG lab with study medication, pulse oximeter and study diary.
- 12 Vital signs include the following: seated blood pressure, pulse, respiratory rate; AE collection refers to spontaneous AEs. Participants who experience systolic blood pressure \geq 160, or diastolic blood pressure \geq 100, or heart rate \geq 120 beats per minute will be further evaluated.
- 13 If there are any responses to individual items at EOS Visit that are more than 4 points worse than baseline exam, CSSA is repeated by telephone at 1 week post EOS Visit.

2 Introduction

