5.2 Exclusion Criteria

Participants are excluded from the study if any of the following criteria apply:

Medical Conditions

1. History of narcolepsy.
2. Clinically significant craniofacial malformation.
3. Clinically significant cardiac disease (e.g., rhythm disturbances, coronary artery disease or cardiac failure) or hypertension requiring more than 2 medications for control.
4. Clinically significant neurological disorder, including epilepsy/convulsions.
5. History of schizophrenia, schizoaffective disorder or bipolar disorder according to Diagnostic and Statistical Manual of Mental Disorders-5 (DSM-5) or International Classification of Disease tenth edition criteria.
6. History of attempted suicide or suicidal ideation within 1 year prior to screening, or current suicidal ideation.
7. History of clinically significant constipation, gastric retention, or urinary retention.
8. Positive screen for drugs of abuse or substance use disorder as defined in DSM-V within 24 months prior to Screening Visit.
9. A significant illness or infection requiring medical treatment in the past 30 days.
10. Clinically significant cognitive dysfunction.
11. Untreated narrow angle glaucoma.
12. Women who are pregnant or nursing.

Prior/Concomitant Therapy

13. History of using oral or nasal devices for the treatment of OSA may enroll as long as the devices are not used during participation in the study.
14. History of using devices to affect participant sleeping position for the treatment of OSA, e.g. to discourage supine sleeping position, may enroll as long as the devices are not used during participation in the study.
15. History of oxygen therapy.
16. Use of medications from the list of disallowed concomitant medications.
17. Treatment with strong cytochrome P450 3A4 (CYP3A4) inhibitors, strong cytochrome P450 2D6 (CYP2D6) inhibitors, or monoamine oxidase inhibitors (MAOI) within 14 days of the start of treatment, or concomitant with treatment.

Prior/Concurrent Clinical Study Experience

18. Use of another investigational agent within 90 days or 5 half-lives, whichever is longer, prior to dosing.

Diagnostic Assessments

19. ESS total score > 18.
20. Central apnea index > 5/hour on baseline PSG.
21. Periodic limb movement arousal index >15/hour on baseline PSG.
22. Hepatic transaminases >3X the upper limit of normal (ULN), total bilirubin >2X ULN (unless confirmed Gilbert syndrome), serum creatinine >2X ULN.

Other Exclusions

23. <6 hours typical sleep duration.

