7.2 Stopping Criteria

7.2.1 Individual Participant Stopping Criteria

- Incidents of abuse, diversion, or misuse of the study treatment.
- Incidents of clinical significance: hallucinations, amnesia, delusional thinking, delirium, manic symptoms, aggressive behavior, suicidality, homicidality, agitation, confusion, or convulsions/seizures.
- Participants reporting any SAE.
- Acute urinary obstruction.
- Any other AE that in the judgment of the Investigator necessitates the participant stopping to protect participant safety.

Participants discontinued from dosing will undergo end of study procedures with follow-up monitoring of the AE(s) as clinically indicated.

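### CSSA item 17, the score named to monitor suicidality, is first taken after baseline on the final dosing night, too late to inform the Day 6 dose step-up

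*Protocol*

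**What the plan says.** Protocol 8.2 promises a questionnaire to pick up emerging suicidal ideation or behavior. Section 8.2.5 names it: CSSA item 17 "will be used to monitor participants for suicidality during the study (whether or not abuse-related"). A score of 3 or more counts as an adverse event and starts clinical evaluation. Under 8.1.2, investigator judgment that the participant is suicidal starts the same evaluation.

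The CSSA row of the amended Schedule of Activities (protocol 1.3) carries the note "Item 17 of the CSSA is used to assess suicidality". It is marked at Visit 1 (Day -28 to -1), Visit 4 (Day 12 ± 2) and Visit 5. The cells for Visit 2, the placebo nights, at-home dosing and Visit 3 are empty. SAP 6.1 marks the same visits, and SAP 4.10.4 summarizes the CSSA at Visit 4, Visit 5 and, where available, one week later. Footnote 5 of the schedule confirms that the "final night of study treatment dosing is PSG night".

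The plan has other safeguards in the same period:

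- Adverse events are monitored in every column of the amended schedule, including Visit 3.
- Section 8.2.5 adds: "Participants should be monitored appropriately and observed closely for suicidal ideation and behavior". It also asks families and caregivers to report changes.
- The individual stopping criteria in 7.2.1 include "aggressive behavior, suicidality, homicidality, agitation, confusion, or convulsions/seizures".
- On early discontinuation, "all EOS procedures should be performed at the discontinuation visit, within 48 hours of the last study dose", and these include the CSSA.
- Exclusion criterion 6 in 5.2 removes anyone with a "History of attempted suicide or suicidal ideation within 1 year prior to screening, or current suicidal ideation".

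**The concern.** A numeric trigger is useful for an individual's safety if it can be met while dosing can still be changed. Section 8.2.5 asks sites to consider discontinuing participants who show signs of ideation. As scheduled, the item 17 trigger can first be met on a planned post-baseline score when at most one dose remains.

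The largest dose change comes on Day 6, when active-arm participants move from 25/1.5 mg to their assigned dose. No item 17 score is planned between the start of active dosing and that step. The person affected is one who has developed ideation, keeps dosing and does not volunteer it. Schedule footnote 12 limits adverse event collection to spontaneous events, and 8.3.2 prefers open-ended, non-leading questions. Neither puts a direct question about suicidality on the schedule.

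**Working it through.** **Inputs**

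- Dosing sequence: 3 low-dose nights, then 7 assigned-dose nights, 10 in all (schedule, dosing row). Placebo is given on Days 1 and 2, so active dosing starts on Day 3.
- The assigned dose starts on Day 6 (SAP 4.5).
- Visit 4 falls on Day 12 ± 2 and is the last dosing night.
- Visit 3 is a daytime, in-person visit on Day 6. Footnote 6 adds: "Can occur as late as day as Day 7, if necessary for scheduling".
- Planned size: 35 per arm, with arms 75/5, 75/1.5, 25/5 and placebo.

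**The plan's own count.** Days 3 to 12 inclusive give 12 − 3 + 1 = 10 active nights, which matches the stated 3 + 7 = 10.

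**Formulas.** Let v be the day of Visit 4 and d the day of Visit 3. I assume that daytime Visit 3 precedes that night's dose.

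- Active doses in total: v − 2
- Active doses before the first post-baseline score, as planned: at least v − 3. This is a minimum because the schedule does not say whether the Visit 4 CSSA comes before that night's dose.
- Active doses before a Visit 3 score: d − 3
- Active doses still to come after Visit 3: v − d + 1
- At-home nights on the assigned dose: v − 6

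| | v = 10 | v = 12 | v = 14 |
|---|---|---|---|
| Doses before first score, as planned | 7/8 (88%) | 9/10 (90%) | 11/12 (92%) |
| Doses before score, Visit 3 on Day 6 | 3/8 (38%) | 3/10 (30%) | 3/12 (25%) |
| Doses before score, Visit 3 on Day 7 | 4/8 (50%) | 4/10 (40%) | 4/12 (33%) |
| Doses still to come after a Day 6 score | 5 | 7 | 9 |
| Doses still to come after a Day 7 score | 4 | 6 | 8 |
| At-home assigned-dose nights | 4 | 6 | 8 |

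**Interval between the two scores.** There is no Day 0. Visit 1 on Day -1 is v days before Visit 4, and Visit 1 on Day -28 is v + 27 days before. With v = 12 this is 12 to 39 days; across all windows it is 10 to 41 days.

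**Who steps up on Day 6.** At least one component rises in 3 × 35 = 105 participants. Atomoxetine goes from 25 to 75 mg (75/25 = 3 times) in the 75/5 and 75/1.5 arms, 2 × 35 = 70. The 25/5 arm increases oxybutynin only.

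**What a Day 6 score leaves open.** It follows three nights of 25/1.5. The at-home assigned-dose nights with no score before Visit 4 number 6 (4 to 8), exactly as now. A Day 7 score follows one assigned dose, leaving 5 (3 to 7) at-home nights.

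**The case against.** The best case against the point has four parts.

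First, no stated requirement is broken. Section 8.2.5 gives no frequency, and scores at screening, end of dosing and end of study fit its wording. This stands: the schedule does not contradict the text, and the point is about timing.

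Second, the period is covered. Staff see participants in person at Visit 3, and investigator judgment can start the same evaluation without a score. A reader might infer from the empty cells that suicidality goes unmonitored during at-home dosing. The documents do not support that, given the safeguards listed above. What remains is that none of them is a scheduled direct question. The stopping criterion acts only on what has been detected, and the discontinuation CSSA comes after the last dose.

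Third, a Day 6 score says nothing about ideation that emerges on the assigned dose. This also stands. A reader might take the fall from 90% to 30% as closing the gap; it does not, because the later at-home nights stay unscored. A Day 7 visit misses the step-up itself.

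Fourth, the precedents are weak. Amendment 1 put prior and concomitant medication monitoring in the Visit 3 column, and a reader might see that as precedent for a new Visit 3 assessment. The stated reason is that this monitoring takes place at Visit 3, so it reads as aligning the schedule with existing practice. Leaving questions 4 and 5 out at baseline (8.1.2) shows that the CSSA need not be given whole, but not that one item can stand alone. The item's wording and recall period are not in the documents. They should be checked in the Study Reference Manual before item 17 is used alone.

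**Conclusion.** The point holds as one of timing. The score named to monitor suicidality is first scheduled after at least 9 of 10 active doses (7 of 8 to 11 of 12), so it cannot inform the Day 6 step-up. That step triples atomoxetine in 70 of 105 active-arm participants. The 70 is the more relevant number, because the boxed warning cited in 8.2.5 is for atomoxetine, and it concerns children and adolescents.

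Priority is modest. Section 8.2.5 reports no increased risk in adults, recent or current ideation is excluded, and no event rate is given, so no number of cases can be claimed. No efficacy conclusion is affected. Visit 4 already supplies an item 17 score on the assigned dose for the comparison between arms; a Day 6 score would serve individual safety only.

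The counts assume full arms of 35, nightly dosing without gaps, and a three-night run-in. SAP 4.5 shows a +2 window on the run-in days. A longer run-in would delay the step-up but would not change the number of active doses taken before the first score.

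**What to change.** In the CSSA row of protocol 1.3 and SAP 6.1, mark Visit 3 with this note: *item 17 only, asked by clinical staff of all participants before that night's dose; schedule on Day 6 where possible so that it precedes the first assigned dose.* A score of 3 or more is then handled under 8.2.5 before the next dose. SAP 4.10.5 already tabulates by study visit, so Visit 3 is added there; SAP 4.10.4 can stay as it is.

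The cost is a protocol amendment with IRB approval (10.1.1), a one-item eCRF change, the matching SAP edit and a little staff time at a visit that already takes place. If the consent form is revised, 10.1.3 requires current as well as later participants to sign it.
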